# Methodology, delivery and sample size

Methodology and delivery

The Programme will be delivered in partnership with the NHS. The end-to-end patient journey is summarised in Figure 1 below.

Recruitment and sample collection will take place in NHS Trusts. All babies will undergo whole genome sequencing and receive results following analysis for a defined list of rare conditions that are treatable in childhood. Condition selection is governed by a set of agreed principles established by an expert Working Group following expert and public consultation, and under the oversight of an NHS Clinical Assurance Group that ensures relevant expert sign off of conditions, the availability of treatments and the capacity of clinical pathways. Modelling indicates that our approach will achieve a true positive to false positive ratio similar to existing newborn screening services.

[figure not shown]

11

Figure 1 - The participant experience

Comparator data will be drawn from age and gender matched children in two groups:

- a population comparator group of babies born at non-participating Trusts during the recruitment period of the study
- a rare conditions comparator group of children diagnosed with the study conditions nationally
  as identified through specialist clinical services and laboratories over a multi-year period with
  similar diagnostic genomic testing availability to the study period

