- Initial approach: a member of the site study team may pro-actively approach parents from around 20 weeks' gestation to invite them to participate in the study. This may include when they are attending their 20-week anomaly scan appointment where an approach may be made in the scan waiting room. Site study teams will be aware of study exclusion criteria to minimise approaching parents who would not be eligible to take part. Parents will be given a copy of the study leaflet or patient information sheet (depending on the amount of time available to have an initial discussion about the study), and signposted to the study microsite/digital information sheet. Parents will be asked for permission to be contacted by the site study team to further discuss participation. It should be noted that in some cases potential participants may be approached at a later stage in pregnancy, and in other those in early pregnancy who have heard about the study and expressed interest in participating may provide consent.
- Time to consider: parents will be given time to consider participation in the study by reviewing hard-copy and digital resources (see section below), and to ask any questions they have about the study by speaking with a member of their study team. Parents may decide to take part on the same day when they are initially approached about the study, or may want more time to consider. Participant materials and study teams will highlight the importance of discussing participation with others with parental responsibility such as the baby's other parent (where available), as well as family members or other individuals helping to make decisions about their baby. Although only one person with legal parental responsibility would consent to their baby taking part in the study, where parents have different opinions about agreeing to take part, it will be recommended that they do not participate. This is to

emphasise the importance that both parents have a say in the interests of familial decision-making and in the context of genomics. Drop-in information sessions (run face to face or virtually at site or national level) may also be used to provide further information about the study.

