# Pathway for recording consent post-partum

The Generation Study does not provide a formal post-partum consent pathway. However, we acknowledge the practicalities associated with conducting a witnessed consent close to birth and do allow for delayed recording of consent in the Generation Study Portal for mothers / birthing parents who deliver after having a verbal consent conversation antenatally (as detailed below).

This situation can arise, for example, when a mother / birthing parent has been advised to take time to reflect on the participation decision after a face to face discussion in late pregnancy, or when registering their interest for participation on the study website close to birth.

Parents should be made aware that participation may not be possible unless:

- 1. A consent conversation has been completed (to the extent that the 11 consent statements in the consent form have been discussed),
- 2. The birthing parent has been advised to take time to consider participation (acknowledging that this will vary person to person), and
- 3. The birthing parent has verbally expressed a willingness to participate. If an initial introduction to the study has been made but a consent conversation covering the main points in the consent form has not been completed by the time the baby is born (as outlined in the point above), the birthing parent would not be eligible to participate in the study. Potential participants should be made aware of this risk upfront.

Process

- A verbal expression of willingness to participate should be recorded in the patient notes to ensure visibility for the wider ward team and in line with usual expectation for clinical research interactions.
- If the baby is delivered whilst the potential participant (who has verbally expressed interest in participating see point above) is reflecting on their decision, a cord blood sample should still be taken. Ideally, verbal ratification from the participant at the time should be sought before sampling. Otherwise staff should follow-up as soon as reasonably possible with the birthing parent to affirm their choice to consent.
- The sample can be refrigerated as per standard protocol

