# 8. Sample Collection

## Introduction

The Generation Study sampling strategy is based on the results of our feasibility study (see Section 4). This study demonstrated that cord blood was an ideal sample type. One sample of cord blood will be collected from each baby, this may take place in hospital, or at home if it is a home birth. NHS England encourages mothers/birthing parents to deliver at home where it is safe to do so. 161,162

In some cases, obtaining a cord blood sample may not be possible, for instance where there is an emergency c-section. However, it is important to facilitate the collection of a sample where it is safe for the baby. In these cases a heel prick sample may be taken or, if the baby is admitted, a sample may drawn from an indwelling line.

Importantly, the procurement of any sample other than cord blood is at the discretion of the research teams, in collaboration with clinical teams. Safety of the baby is paramount. Parents should be informed of the risks of sampling in advance, and verbal parental consent for a secondary sample (heel prick or blood from an indwelling line) should be sought. Secondary samples must be procured as close to birth as possible. If this is not possible, recruiting centres will be asked not to carry out heel prick sampling in the home context until after the Newborn Blood Spot test has been taken, to avoid the risk that parents might conflate the Generation Study sample with the Newborn Blood Spot standard of care.

**For sites:** Please refer to the separate study sampling guide for recruiting sites for details relating to sample collection, local processing and shipping. All NHS staff at recruiting sites handling study samples should adhere to the guidelines in this supporting document.

More detail on each sample type is provided below:

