## Population comparator group

All children born at selected non-participating Trusts during the recruitment period of the study. Trusts will be selected on the basis of matching characteristics including level of diversity of patient reported ethnicity and socio-economic deprivation and the rural vs urban nature of the area served.

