# Data from Healthcare records, Longitudinal data sources and from National and Local data sets on the Population and Rare conditions comparator groups

• For each of the following areas, data from study participants will be compared with data from the both the Population comparator group and the Rare conditions comparator group.

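### The population comparator takes all births, while participants are singletons consented before birth; matching on age and gender alone is likely to make participants look like lower users of care

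*Protocol*

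**What the plan says.** **Entry to the study.** Section 6 (Inclusion and exclusion criteria) requires a singleton birth and excludes multiple births in the initial rollout. It sets no gestation limit. Babies with complicated births or NICU admission are eligible, with sampling decided case by case. Under Section 7, a site team "may pro-actively approach parents from around 20 weeks' gestation". "The Generation Study does not provide a formal post-partum consent pathway"; if the study has been introduced but the consent conversation "has not been completed by the time the baby is born (as outlined in the point above), the birthing parent would not be eligible". Only the recording of consent may follow birth.

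**Sampling.** Section 8 makes cord blood the preferred sample and accepts that "obtaining a cord blood sample may not be possible, for instance where there is an emergency c-section". Heel prick and, for admitted babies, blood from an indwelling line are discretionary back-ups. For the heel prick, the outer limit for taking and registering the sample is 28 days.

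**Comparator.** The Synopsis (Methodology, delivery and sample size) states: "Comparator data will be drawn from age and gender matched children in two groups". Section 12 (Population comparator group) takes "All children born at selected non-participating Trusts during the recruitment period of the study". Trusts are chosen for similarity in ethnic diversity, deprivation and rural or urban setting. At the level of the child, age and gender are fixed, and Section 12 (Data on comparator groups) mentions location and ethnicity as examples of further matches under consideration.

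**Use.** In Appendix A (Cost effectiveness and positive and negative impacts, Data sources), for each area listed, "data from study participants will be compared with data from the both the Population comparator group and the Rare conditions comparator group". The healthcare-cost heading also names the population group.

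**The concern.** The conditions for entering the cohort have no counterpart in the comparator. A parent who delivers at 28 weeks has had about 8 weeks since the usual first approach in which to complete the conversation; one who delivers at 40 weeks has had about 20. Twins and higher multiples are absent from participants under the current criteria but present among all births. Matching on chronological age and gender removes neither difference.

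If babies born early or as multiples use more care in infancy, an all-participants against all-births contrast starts with a deficit in use that has nothing to do with screening. The deficit points in the direction that favours screening. Cost effectiveness is a secondary outcome and the stated audience is policy makers, so a selection artefact could be read as a saving.

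**Working it through.** The protocol gives no figure for this contrast. Its 105,000 sample size concerns the incidence estimate and has no bearing here.

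**1. The filters side by side**

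| Condition | Participants | Population comparator |
|---|---|---|
| Singleton | Required (Section 6) | Not stated |
| Consent conversation complete before birth | Required (Section 7) | Not applicable |
| Usable sample registered | Required (Section 8) | Not applicable |
| Gestation, plurality or mode of birth in the matching | – | Not named (Section 12) |

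**2. How the consent rule could act by gestation (illustration).** Assume that consent accrues at a constant rate from 20 weeks and reaches a share c by 40 weeks. The chance of entry at gestation g, relative to 40 weeks, is [1 − exp(−h(g − 20))]/c, with h = −ln(1 − c)/20. With c = 0.5, h = 0.0347:

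- 28 weeks: (1 − exp(−0.277))/0.5 = 0.242/0.5 = 0.48 (0.44 to 0.55 for c = 0.3 to 0.7)
- 34 weeks: (1 − exp(−0.485))/0.5 = 0.384/0.5 = 0.77 (0.74 to 0.81)

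If most consent is given at or before the 20-week scan, which Section 7 allows, both ratios move towards 1.

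**3. The sampling filter.** In the feasibility study (Section 4, Table 2), cord collection failed in 35% of emergency sections and 20% of all births. If a share q of missed cord samples is recovered by a back-up sample, inclusion of emergency sections relative to the average is (0.65 + 0.35q)/(0.80 + 0.20q):

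- q = 0: 0.65/0.80 = 0.81
- q = 0.5: 0.825/0.90 = 0.92
- q = 0.8: 0.93/0.96 = 0.97
- q = 1: 1.00

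**4. Effect on mean care use with no screening effect.** Let s be the comparator's share of high-use births (for example preterm), r their relative chance of entry, and k their use relative to other babies. The share among participants is s′ = sr/(1 − s + sr), and the apparent ratio of mean use is [1 + s′(k − 1)]/[1 + s(k − 1)]. None of s, r or k is in the documents. The assumed ranges are s = 6–10%, r = 0.5–0.9 and k = 3–10.

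- Central (s = 0.08, r = 0.7, k = 5): s′ = 0.056/0.976 = 0.0574; ratio = 1.2295/1.32 = 0.93
- Largest bias (0.10, 0.5, 10): s′ = 0.05/0.95 = 0.0526; ratio = 1.474/1.90 = 0.78
- Smallest bias (0.06, 0.9, 3): s′ = 0.054/0.994 = 0.0543; ratio = 1.109/1.12 = 0.99
- r = 1: ratio = 1.00

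The ratio is below 1 whenever r < 1 and k > 1. Only its size depends on the assumed values.

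**The case against.** **The matching list is open.** Section 12 offers location and ethnicity as examples, and detailed analytical plans are left to an Evaluation Protocol that is not shown. This stands against saying that the bias will occur or that gestation has been ruled out. It does not remove the point: the comparator's membership and its two fixed matching factors are set in this protocol, and membership is all births.

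**The itemised measures are narrower.** In Appendix A, service use, interventions, morbidity and mortality are described for true positives against children with comparable diagnoses. The cost item also draws comparators from specialist services, registries, the 100,000 Genomes Project or birth cohorts, and the economic model in Section 13 uses condition-specific inputs. This stands and limits the reach of the point. But the lead statement in the same appendix keeps the population group for every area, and the service-use item announces two groups before describing one, so a whole-cohort contrast remains planned on the page.

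**Sampling may filter very little.** The 35% and 20% figures are cord-collection failures in the feasibility study, where collection improved over time, and not losses from this study. Heel-prick and indwelling-line back-ups could bring relative inclusion close to 1.00. This stands; the point rests mainly on the consent and singleton rules.

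**A stronger reading.** A reader might infer that the artefact must exceed any real effect, because true positives are only 0.65/572 = 0.114% of babies. That comparison needs a preterm deficit and bed-day figures for preterm babies and for true positives. The documents give none of these, and report no preterm participation at all.

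**Conclusion.** The point holds in a limited form. The population comparator is not restricted to births that could have entered the study, and the fixed matching factors do not carry gestation or plurality. Whole-cohort contrasts of service use or cost with that group are likely to be biased towards lower use in participants.

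The direction rests on two assumptions: that early births enter less often, which is inferred from the consent rule, and that early or multiple births use more care. The size cannot be derived from the documents; 0.78 to 0.99 is an illustration under assumed inputs. The primary count of screen-identified diagnoses is untouched, and the true-positive against comparable-diagnosis contrasts are not the main target. It would go too far to conclude that the study's cost-effectiveness result is invalid, since the economic model does not rest on this contrast.

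**What to change.** Amend the comparator text in the Synopsis (Methodology, delivery and sample size) and in Section 12 (Data on comparator groups; Population comparator group):

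1. Restrict the population comparator to births that meet those entry criteria which routine data can identify; in particular, singletons for as long as multiple births are excluded from the study.
2. For every whole-cohort contrast, match or standardise on gestational age at birth as well as age and gender. Use mode of birth as a further adjustment or a sensitivity analysis.
3. Name the source of these variables in the list of national data sets in Section 12. One option is to add the Maternity Services Data Set, which Section 13 (Interim Analysis) cites only for recruiting sites and which is not on the comparator list. The linkage described under Longitudinal data sources concerns participants and cannot serve for this.
4. State in Appendix A which areas will in fact be compared with the population group.

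The cost is a wording amendment, one more comparator data set or field, and fewer usable matches at very low gestations.

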### Sample size

The sample size calculation based on current estimates of disease frequency and analytical parameters indicates a sample size of approximately 105,000 newborns to address the primary outcome of the study; details of the sample size calculations are provided in Section 6.

#### **Evaluation**

Programme evaluation aims to develop holistic evidence to drive future policy decisions. It will be carried out in four workstreams: a performance dashboard, an economic model, process evaluation and impact evaluation. Evaluation will be delivered by Genomics England in partnership with an Evaluation Partner and covered by an additional Evaluation Protocol.

Together, the economic modelling and process and impact evaluation will explore research questions in the four broad areas set out above, each with a primary question and multiple secondary questions exploring both positive and negative impacts. Rather than isolated workstreams, these will be interlinked.

### Conclusion

The Generation Study builds on the strong track record that the UK has in genomics, and the recent investments by government, research funders and the NHS in genomic healthcare research and implementation. Delivered in partnership with the NHS, at scale across a national health system, the study is uniquely placed to deliver on its aims to develop evidence for policy makers on whether and how whole genome sequencing should be offered routinely to all newborns while also stimulating vital research and new discoveries.

# 3. Background

### Genomics in healthcare

Genomics - the study of a person's DNA - is playing an increasing role in healthcare. This builds on many decades of foundational discoveries. From Mendel's insights into inheritance, to the elucidation of the structure of DNA by Franklin, Crick and Watson and the invention of the first methods to read the sequence of DNA by Sanger.

More recently, this has been followed by the invention of 'next generation' sequencing technologies that allow sequencing at greater scale and lower cost. This has brought a new era of scientific discovery across a range of health conditions. Paired with the development of supporting analytical and computing capabilities, knowledge bases and laboratory scientific interpretation standard operating procedures, this has widened the range of settings in which genomics is used in routine care.

With the advent of next generation sequencing, health systems now have a number of techniques at their disposal, with different tests used to address different clinical questions. These range from highly targeted tests, such as those that assay for one or a handful of specific genomic variants in one gene, to panel sequencing, typically looking at tens or hundreds of genes, and exome sequencing, which targets the 1-2% of the genome that codes for genes, to whole genome sequencing.

Analysis for next generation sequencing-based tests, and particularly whole exome sequencing (WES) and whole genome sequencing (WGS) means that there is a practical and conceptually useful separation into three different elements:

- 1. **The assay.** The generation of raw sequence data from a sample.
- 2. **The analysis.** The analysis of the data in a given clinical context, using complex analytical algorithms tailored to the clinical context. For example, looking for variation in carefully selected parts of the genome that might be relevant to the clinical context.
- 3. **The result.** The generation of a result and return of the result to the clinician and patient

The recognition of these distinct elements is useful in deciding how to use genomic testing clinically and, critically, explaining to patients and participants the nature of the analysis that is being performed. The three elements can also happen at different times - the data generated from an assay performed for one purpose could be reused to perform a different analysis, for example to answer a different clinical question.

### Diagnostics

In the NHS and other advanced health systems, genomics is now routinely used in diagnostics. It is a mainstay in the diagnosis of rare conditions and in the diagnosis and stratification for treatment in cancer,,. The range of diagnostic settings that it is used in is expanding rapidly, with whole genome sequencing playing an increasing role, particularly in complex rare conditions and certain cancers.

### Predictive and preventative care

The role of genomics in predictive and preventative care is also increasing. This includes its use in 'pharmacogenomics', the use of genomic testing to tailor the choice or dose of medication to avoid harm (for example by avoiding adverse reactions) and to increase efficacy . Testing using polygenic risk scores to identify people at higher risk of common diseases including cardiovascular

disease and certain cancers is the focus of research to understand whether it can be used in routine care to identify those who would benefit from risk lowering treatment or closer surveillance for disease. Highly targeted genomic tests also play a small but increasing role in screening for rare, treatable conditions in newborn babies.

#### Genomics in newborns

The potential value - as well as the risks and complexities - of routine genomic testing, even whole genome sequencing, being routinely offered to all newborn babies has been increasingly discussed in recent years. Areas of potential utility fall broadly in three areas:

- 1. **Newborn screening.** For immediate use as part of newborn screening
- 2. **Supporting research.** To support healthcare research, including to improve newborn screening and to improve diagnosis and support the development of new treatment for rare conditions
- 3. **Life course use in healthcare.** To be stored for future healthcare use during the life course

### Rare conditions

In the UK, a rare condition is defined as affecting fewer than 1 in 2,000 people. There are estimated to be approximately 7,000 rare conditions. This means that while they are individually rare, they are collectively common. It is estimated that 1 in 17 people have a rare condition. They disproportionately affect children, are often medically complex and are a leading cause of mortality and disability in children in high income countries, The rarity of the conditions means that they have historically been hard to diagnose.

For many of these conditions, most benefit is derived if they are detected early, with better outcomes in the pre-symptomatic phases. The importance of an early diagnosis was recognised in the UK government's 2022 Rare Disease Framework.

